8.1.1 Progressive Disease

Progressive disease (PD) is defined according to the international uniform response criteria (Durie et al. Leukemia 20:1467-73, 2006, ERRATUM Durie et al. Leukemia 21:1134, 2007) and requires any of the following, confirmed on two consecutive assessments:

An increase of 25% from lowest response value in any one or more of the following:

- Serum M-component (absolute increase must be ≥ 0.5 g/100 ml) *
- Urine M-component (absolute increase must be ≥ 200 mg per 24 h)
- Only in patients without measurable serum and urine M-protein levels: the difference between involved and uninvolved FLC levels (absolute increase must be >100 mg/l)
- Bone marrow plasma cell percentage (absolute % must be $\geq 10\%$)

And / or:

- Definite development of new bone lesions or soft tissue plasmacytomas or definite increase in the size of existing bone lesions or soft tissue plasmacytomas
- Development of hypercalcemia (corrected serum calcium >11.5 mg/100 ml) that can be attributed solely to the plasma cell proliferative disorder

*: If the starting serum m-protein level is ≥ 5 g/dL an absolute increase of ≥ 1 g/dL, verified on two consecutive measurements, is sufficient to define progressive disease.

The decision as to when to repeat the assessment to document progressive disease will be left at the discretion of the treating physician, there is no need to wait until the next scheduled response assessment.

9 Safety assessments

Safety assessments will consist of monitoring and recording all adverse events and serious adverse events, the regular monitoring of hematology, blood chemistry and urine values, vital signs, ECOG performance status, and the regular physical examinations and ECG assessments.

Adverse events will be assessed according to the Common Toxicity Criteria for Adverse Events (CTCAE) version 4.0. CTCAE v4.03 can be accessed on the NIH/NCI website at (http://ctep.cancer.gov/protocolDevelopment/electronic_applications/docs/ctcae4.pdf)

9.1.1 Adverse events

Information about all adverse events, whether volunteered by the subject, discovered by investigator questioning, or detected through physical examination, laboratory test or other means, will be collected and recorded and followed as appropriate.

An adverse event is the appearance or worsening of any undesirable sign, symptom, or medical condition occurring after starting the study drug even if the event is not considered to be related to study drug. Medical conditions/diseases present before starting study drug are only considered adverse events if they worsen after starting study drug. Abnormal laboratory values or test results constitute adverse events only if they induce clinical signs or symptoms, are considered clinically significant, or require therapy.

The occurrence of adverse events should be sought by non-directive questioning of the patient at each visit during the study. Adverse events also may be detected when they are volunteered by the patient during or between visits or through physical examination, laboratory test, or other assessments. As far as possible, each adverse event should be evaluated to determine:

1. the severity grade (mild, moderate, severe) or (grade 1-4)
2. its relationship to the study drug(s) (suspected/not suspected)
3. its duration (start and end dates or if continuing at final exam)
4. action taken (no action taken; study drug dosage adjusted/temporarily interrupted; study drug permanently discontinued due to this adverse event; concomitant medication taken; non-drug therapy given; hospitalization/prolonged hospitalization)
5. whether it constitutes a serious adverse event (SAE)

All adverse events should be treated appropriately. Such treatment may include changes in study drug treatment including possible interruption or discontinuation, starting or stopping concomitant treatments, changes in the frequency or nature of assessments, hospitalization, or any other medically required intervention. Once an adverse event is detected, it should be followed until its resolution, and assessment should be made at each visit (or more frequently, if necessary) of any changes in severity, the suspected relationship to the study drug, the interventions required to treat it, and the outcome.

Information about common side effects already known about the investigational drug can be found in the Investigators' Brochures for panobinostat and MLN9708 or will be communicated between IB updates in the form of Investigator Notifications. This information will be included in the patient informed consent and should be discussed with the patient during the study as needed.

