Phase II extension: Patients in phase I (median age 65, range 50-73, median previous regimens 5, range 2-10) tolerated treatment without DLT and without non-hematologic severe (grade 3 or higher) adverse event according to CTCAE vs.4.03. Three patients developed grade 3 hematologic toxicities (2 neutropenia, 1 thrombocytopenia). Worst diarrhea was grade 1 (n=6), worst nausea grade 2 (n=1) and 4 additional patients developed transient grade 1 nausea. Other possibly panobinostat or ixazomib related grade 1/2 adverse events included thrombocytopenia (n=5), neutropenia (n=3), fatigue (n=2), anemia (n=2), anorexia (n=1) and arthralgia (n=1).

Median QTcF before treatment start was 405 msec (range 378-430) and increased on average by 4.3% (maximally by 13%). One patient developed transient grade 1 QTcF prolongation to 552 msec. No other cardiac adverse events were observed. Of the 11 patients in phase I, one reached PR, two reached MR, and one had stable disease for 6 months. All patients entered the study with disease refractory to their last regimen, and in two of the responding patients (1PR, 1MR) this included a proteasome inhibitor an IMiD, and a glucocorticosteroid (carfilzomib, pomalidomide, dexamethasone in the MR patient, bortezomib, dexamethasone, lenalidomide in the MR patient). Overall, we are encouraged by activity in extensively pretreated patients and by excellent tolerance of this regimen so far. In phase II we aim to extend the study cohort by an additional 20 patients who will be treated until progression or other reasons for discontinuation arise (7.6.1) to strengthen the safety analysis and obtain a more reliable estimate of activity.

3 Study objectives

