3.2 Secondary Objective

- Assess response and clinical benefit response rates according to international uniform response criteria and adapted EBMT criteria, respectively (see under 8.1)
- Assess progression-free survival (PFS) and overall survival (OS)

4 Study endpoints:

4.1 Primary endpoints:

- Dose limiting toxicity (phase I) and tolerance according to CTCAE vs. 4.03 (phase I and II)

4.2 Secondary endpoints:

- Response to panobinostat, dexamethasone, ixazomib (MLN9708) will be assessed according to international uniform response criteria and clinical benefit response according to modified EBMT response criteria, comparing myeloma panels obtained at the beginning of each cycle that include SPEP, 24 h UPEP, serum and urine IFEs, and serum free light chains to results at screening. In addition a baseline bone marrow exam and skeletal survey will be obtained and repeated as clinically indicated and for assessment of complete remission (bone marrow).
- Progression-free survival will be measured from study entry to progression or death of any cause, whichever comes first.

- Overall survival for all will be measured from study entry to death from any cause.

5 Overall study design, treatment cycles, and study duration

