9) Thyroid function tests should be obtained at study entry, at about 3 months from study entry, ideally after the third 28-day cycle, whenever there is clinical suspicion for hypothyroidism, and at the completion of this study unless it has been obtained within 30 days prior to study exit.

10) Weekly CBC/diff, CMP, and magnesium until completion of cycle 2, then as clinically indicated

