10.2 Millennium Instructions for rapid notification of serious adverse events

All serious adverse events (SAEs) (regardless of expectedness or causality) must be reported to Millennium Pharmacovigilance (or designee). See also Novartis Instructions for rapid notification of serious adverse events for the reporting of SAEs.

The sponsor-investigator is responsible to meet all regulations and requirements applicable to the sponsor-investigator.

Adverse events (AEs) may be spontaneously reported by the patient and/or in response to an open question from study personnel or revealed by observation, physical examination, or other diagnostic procedures must be reported to Millennium Pharmacovigilance (or designee). Any clinically relevant deterioration in laboratory assessments or other clinical finding is considered an AE. When possible, signs and symptoms indicating a common underlying pathology should be noted as 1 comprehensive event. For serious AEs, the investigator must determine both the intensity of the event and the relationship of the event to study drug administration. For serious pretreatment events, the investigator must determine both the intensity of the event and the relationship of the event to study procedures.

This is an investigator-initiated study. The principal investigator, [name] (who may also sometimes be referred to as the sponsor-investigator), is conducting the study and acting as the sponsor. Therefore, the legal/ethical obligations of the principal investigator include both those of a sponsor and those of an investigator.

Regardless of causality, SAEs and serious pretreatment events (as defined in Section 10.7) must be reported by the sponsor- to the Millennium Pharmacovigilance or designee by faxing the SAE Report using the US FDA MedWatch 3500A Form :

Fatal and Life Threatening SAEs within 24 hours but no later than 4 calendar days of the sponsor-investigator's observation or awareness of the event

All other serious (non-fatal/non life threatening) events within 4 calendar days of the sponsor-investigator's observation or awareness of the event

The SAE report must include at minimum:

- **Event term(s)**

- **Serious criteria**

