- **Intensity of the event(s):** Sponsor-investigator's or sub-investigator's determination. Intensity for each SAE, including any lab abnormalities, will be determined by using the NCI CTCAE version 4.0 specified in the protocol, as a guideline, whenever possible. The criteria are available online at <http://ctep.cancer.gov/reporting/ctc.html>.
- **Causality of the event(s):** Sponsor-investigator's or sub-investigator's determination of the relationship of the event(s) to study drug administration.

In the event that this is a multisite study, the sponsor-investigator is responsible to ensure that the SAE reports are sent to Millennium Pharmacovigilance or designee from all sites participating in the study. Sub-investigators must report all SAEs to the sponsor-investigator so that the sponsor-investigator can meet his/her foregoing reporting obligations to Millennium Pharmacovigilance. Millennium Pharmacovigilance (or designee) may request follow-up information to a reported SAE or serious pretreatment event, which the sponsor-investigator will be responsible for providing to Millennium Pharmacovigilance or designee.

Millennium will provide a sample SAE Report Form representative of the information Millennium Pharmacovigilance may request in follow-up.

Planned hospital admissions or surgical procedures for an illness or disease that existed before the patient was enrolled in the study are not to be considered AEs unless the condition deteriorated in an unexpected manner during the study (e.g., surgery was performed earlier or later than planned).

For both serious and nonserious AEs, the investigator must determine both the intensity of the event and the relationship of the event to study drug administration. For serious pretreatment events, the investigator must determine both the intensity of the event and the relationship of the event to study procedures.

Intensity for each AE, including any lab abnormality, will be determined by using the NCI CTCAE, version 4.0 as a guideline, whenever possible. The criteria are available online at <http://ctep.cancer.gov/reporting/ctc.html>

Relationship to study drug administration will be determined by the investigator or sub-investigator by responding yes or no to the question: Is there a reasonable possibility that the AE is associated with the study drug(s)?

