13.1.1.2 Safety

Data from all subjects who receive any protocol therapy will be included in the safety analyses. Subjects who entered the study and did not receive any protocol therapy and had this confirmed, will not be evaluated for safety. Adverse events will be recorded during the entire study, weekly during the first cycle, and at the start of each cycle for subsequent cycles. Toxicity will be graded according to CTCAE v.4.0 whenever possible and reported in a descriptive way.

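### Whether an asymptomatic, untreated grade 3 blood count enters the primary CTCAE tolerability endpoint is left to investigator judgment, because the adverse event definition has no grade threshold and no table from laboratory values is planned

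*Combined protocol and SAP*

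**What the plan says.** Section 4.1 gives the primary endpoint as "Dose limiting toxicity (phase I) and tolerance according to CTCAE vs. 4.03 (phase I and II"). DLT applies to phase I only, so phase II rests on CTCAE tolerance alone.

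The rule for laboratory values is in section 9.1.1: "Abnormal laboratory values or test results constitute adverse events only if they induce clinical signs or symptoms", are judged clinically significant, or need treatment. Section 10.2 has a similar test: "Any clinically relevant deterioration in laboratory assessments or other clinical finding is considered an AE". Neither names a CTCAE grade. Section 10.2 also says how events are graded: "Intensity for each AE, including any lab abnormality, will be determined by using the NCI CTCAE, version 4.0 as a guideline, whenever possible".

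The planned analysis in section 13.1.1.2 is one sentence: "Toxicity will be graded according to CTCAE v.4.0 whenever possible and reported in a descriptive way".

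Weekly counts and chemistry run, by footnote 10 to Table 8-1, "until completion of cycle 2, then as clinically indicated". Later scheduled counts fall on day 1 of each cycle and at study exit.

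The phase II rationale in section 2 reports of phase I: "Three patients developed grade 3 hematologic toxicities (2 neutropenia, 1 thrombocytopenia"). The same paragraph lists grade 1/2 thrombocytopenia (5), neutropenia (3) and anaemia (2) among the adverse events.

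**The concern.** The endpoint and the recording rule use different criteria. CTCAE assigns a grade to a neutrophil or platelet count from the number alone; Table 7-4 itself defines grade 4 by count. Section 9.1.1 asks instead whether the value caused symptoms, mattered clinically or was treated. If the safety table is built from recorded adverse events, a value that is grade 3 by CTCAE can be absent because someone judged it unimportant.

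This matters because myelosuppression is the severe toxicity to expect. In the weekly single-agent ixazomib study in section 1.3.9 (52 patients, mixed doses), drug-related grade 3 or higher thrombocytopenia was 38% and neutropenia 17%. In this trial's own phase I, section 2 reports no severe non-haematologic event, so all the grade 3 toxicity it reports was haematologic. Section 2 also says that phase II is meant to strengthen the safety analysis.

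**Working it through.** No figure in the plan depends on this point, so there is none to reproduce. The check follows one event, an asymptomatic, untreated grade 3 neutropenia or thrombocytopenia in mid-cycle, through each provision that could capture it.

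| Provision | Does it capture the event? |
|---|---|
| 9.1.1, symptoms | No, by assumption |
| 9.1.1, requires therapy | No, by assumption. Growth factor is permitted for severe neutropenia (7.7) but not mandated |
| 9.1.1, considered significant | Only if the investigator so judges |
| 10.2, clinically relevant deterioration | Again a judgment |
| 10.2, grading of intensity | Grades what is already an adverse event; does not make a value one |
| 5.4, DLT (phase I) | No. The count criterion is grade 4 not resolving within 7 days |
| Table 7-4, dose modification | No row. The haematology rows are grade 4 thrombocytopenia, grade 4 neutropenia and febrile neutropenia (ANC below 1.0) |
| 7.4, new cycle | Only if the count is still low on day 1 (ANC below 1.0 or platelets below 50 × 10⁹/L), when the cycle is delayed |
| 13.1.1.2, safety analysis | No tabulation by laboratory value is specified |

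The two judgment tests are the only routes left for a count that has recovered by day 1.

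**Phase I figure.** 3/11 = 27.3%, exact (Clopper-Pearson) 95% interval 6.0% to 61.0%.

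**Illustration of size.** The documents give no fraction f of affected patients who go unrecorded, so f is an assumption. Take 3/11 as the true patient-level rate in the 20 phase II patients.

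Expected recorded count = 20 × (3/11) × (1 − f):
- f = 0: 5.5 patients (27.3%)
- f = 0.25: 4.1 patients (20.5%)
- f = 0.50: 2.7 patients (13.6%)

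Probability that at least one patient is missed = 1 − (1 − (3/11) × f)^20:
- f = 0.25: 1 − (1 − 0.068)^20 = 76%
- f = 0.50: 1 − (1 − 0.136)^20 = 95%

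**Limits on any laboratory-based remedy.** After cycle 2 the scheduled on-treatment count is on day 1, and a new cycle needs ANC of at least 1.0 and platelets of at least 50. Nadirs between visits may never be measured, and no derivation can recover them. Section 6.1.2 also admits patients with ANC of 1.0, platelets of 70 or haemoglobin of 8 g/dL. Raw worst grades would therefore count some pre-existing cytopenia as toxicity.

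**The case against.** The strongest reply is the trial's own record. Phase I reported all three grade 3 cytopenias and also grade 1/2 cytopenias as adverse events, so laboratory grades appear to have been counted in practice. Section 9.1.1 has three alternative routes and excludes no grade 3 count; the same section names laboratory tests as a way to detect adverse events. Low counts on day 1 delay the cycle and leave a trace. Section 7.4 allows growth factor to reach the ANC threshold, Table 7-4 raises its prophylactic use when neutrophils fall below 1.0, and such use meets the therapy condition. Section 7.6 expects additional blood testing by standard practice. The DLT criteria in section 5.4 have their own triggers for grade and duration, transfusion or growth factor, and fever. The study is small, single-arm and descriptive, and the word toxicity in section 13.1.1.2 could be read to include laboratory values.

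Most of this stands, and it narrows the gap to the asymptomatic, untreated mid-cycle episode that recovers by day 1. It does not close it: good phase I practice is not a written rule, and section 13.1.1.2 does not say that laboratory values are graded directly.

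A reader might go further and infer that grade 3 cytopenia is in fact under-counted, that 3/11 could have read 0/11, that the two sites record differently, or that phases I and II are not comparable. The documents support none of these. All three phase I events were reported, the amendment summary lists no change to section 9.1.1, and nothing describes recording by site. Sparse counts after cycle 2 are a scheduling choice, not a result of the adverse event definition.

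**Conclusion.** The point holds as a gap in the written rule. For a value-graded toxicity within the primary endpoint, sections 9.1.1 and 10.2 leave inclusion to judgment, and section 13.1.1.2 adds no analysis that bypasses it. The loss is permitted, not demonstrated, and its size cannot be estimated from the documents. The range of 4.1 to 2.7 recorded patients against 5.5 expected rests on an assumed unrecorded fraction of 25% to 50%, and on a phase I rate that has a wide interval and pools 11 patients over two dose levels.

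The DLT component is largely unaffected. Section 10.3 was not available for this check, so a relevant rule there cannot be excluded. This is a worthwhile, inexpensive improvement; it does not undermine the trial.

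**What to change.** In section 13.1.1.2, add a tabulation of the worst post-baseline CTCAE 4.03 grade per patient for haematology and chemistry, for both phases:

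- Derive grades from the count and chemistry results already collected under Table 8-1, whether or not the value was recorded as an adverse event.
- Show each as a shift from baseline grade, so that cytopenia present at entry is not counted as new toxicity. This fits section 9.1.1, which counts pre-existing conditions only if they worsen.
- Present cycles 1-2 (weekly counts) separately from later cycles (scheduled on day 1, otherwise as clinically indicated), and state that later nadirs may be unsampled.

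Keep the section 9.1.1 rule for adverse event reporting. No visit, dose or management rule changes. The cost is some data entry and programming, and a toxicity rate that may be less favourable than one based on recorded events alone.

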9.1.2 Vital signs

Vital sign assessment consists of height (first visit), pulse, blood pressure, respiration rate, temperature and weight. Blood pressure, pulse and respiration rate should be measured on patients after at least 3 minutes in the sitting position

9.1.3 Physical examination

Physical examination will be performed which must comprise a total body examination (general appearance, skin, neck, including thyroid, eyes, ears, nose, throat, lungs, heart, abdomen, back, lymph nodes, extremities and basic nervous system).

Significant findings made after the start of study drug which meet the definition of an Adverse Event must be recorded.

9.1.4 Laboratory evaluations

Laboratory evaluation should be done at baseline (within ≤ 72 hours prior to dosing prior to the first administration of study drugs, during the course of the study and at the time of the study treatment completion visit. Results must be reviewed prior to administering panobinostat (LBH589) and ixazomib (MLN9708). More frequent examinations may be performed if medically indicated; results should be recorded.

Hematology

Hematology must include hemoglobin, hematocrit, platelets, total white blood cell count (WBC) and differential. The coagulation profile includes a prothrombin time or International Normalized Ratio (INR) and activated partial thromboplastin time.

Blood chemistry

Biochemistry includes the following parameters: BUN, creatinine, sodium, potassium, chloride, CO₂ (HCO₃), glucose, calcium, albumin, total protein, total bilirubin, alkaline phosphatase, AST/SGOT, ALT/SGPT, and magnesium (where indicated in 8). If total bilirubin is greater than the upper limit of normal, direct and indirect bilirubin should be performed.

Thyroid function test

Thyroid Stimulating Hormone (TSH), free T3, and FTI will be measured at baseline, about 3 months after study entry (+/- 14 days), at the study completion, and as deemed clinically necessary during the course of the study.

9.1.5 Serum pregnancy test

All females of childbearing potential should complete a serum pregnancy test within 7 days prior to the administration of study drugs on day 1 of cycle 1. The pregnancy test should be repeated in week 1 of every cycle (except for cycle 1). Postmenopausal women must have been amenorrheic for ≥ 12 months in order to be considered “of non-childbearing potential”.

